7.0 STUDY ASSESSMENTS AND PROCEDURES

7.1 Study Calendar and Assessment Schedule

All visits should be +/- 7 business days with the exception of day 1 of cycle 1.

Procedures	≤ 14 days prior to registration[†]	Treatment				Follow-up	
		Doses 1-4 (Every week – Week 1, 2, 3, 4)	Doses 5-8 (Every week – Week 5, 6, 7, 8)	Doses 9-12 (Every 4 weeks - Week 12, 16, 20, 24)	Treatment withdrawal	1,3, 6 months following last ofatumumab dose	9, 12, 15, 18, 21, 24 months following last ofatumumab dose
Medical History	X						
Disease History	X						
Therapy History	X						
Efficacy Assessments							
¹ Bone marrow/ aspirate biopsy	X					X	
² CT/PET	X					X	X
Safety Assessments							
³ Physical Exam or Evaluation	X	³ X	³ X	³ X		X	X
³ ECOG	X	³ X	³ X	³ X		X	X
Height	X						
Weight	X					X	X
Vital Signs	X	X	X	X		X	
12-lead ECG	X						
Adverse Events		X	X	X	X	X	X
⁴ FFP (2 units)		⁴ X	X	X			
Dispense Study Medication							
Ofatumumab		X	X	X			
Lab Assessments							
⁵ Hematology	X	X	X	X		X	X
⁶ Chemistry	X	X	X	X		X	X
⁷ Liver chemistry	X	X	X	X			
⁸ Complement levels	X	X		X		X	X

Procedures	< 14 days prior to registration[†]	Treatment				Follow-up	
		Doses 1-4 (Every week – Week 1, 2, 3, 4)	Doses 5-8 (Every week – Week 5, 6, 7, 8)	Doses 9-12 (Every 4 weeks - Week 12, 16, 20, 24)	Treatment withdrawal	1,3, 6 months following last ofatumumab dose	9, 12, 15, 18, 21, 24 months following last ofatumumab dose
⁹ B-cells, IgG, IgA and IgM	X					X	
¹⁰ HIV Test	X						
¹¹ Serum Pregnancy Test	X						
Hepatitis B&C*	X						X
Survival	X					X	X

***REQUIRED- Subjects who are HBcAb positive** must undergo at least every 2 month HBV DNA PCR testing during the treatment course. Monitoring must also occur during the follow-up period for a minimum of 6 months after the last dose as long as the subject remains in the study at a minimum frequency of every 2 to 3 months.

[†] Bone marrow/aspirate biopsy and CT/PET performed within 28 days of registration.

1. BM biopsy will be performed for staging at baseline and if clinically warranted after completion of therapy. If the BM biopsy is positive at baseline it must be repeated once to confirm CR. This will include flow cytometry for minimal residual disease (MRD) status. Bone marrow (or peripheral blood if bone marrow is unavailable must be sent to the cytogenetics laboratory for analysis. If the BM biopsy is negative at baseline, it will not be repeated.

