7.2 Efficacy

Efficacy analyses will be performed on data from the Intent-to-Treat Population.

Definition of Response

Response criteria	NCI-WG National Cancer Institute – Working Group	IWCLL International Workshop on Chronic Lymphocytic Leukemia
Complete Response (CR):		
Physical exam (nodes, and/or liver, spleen)	Normal	Normal
Symptoms	None	None
Lymphocytes ($\times 10^9/L$)	≤ 4	<4
Neutrophils ($\times 10^9/L$)	≥ 1.5	
Platelets ($\times 10^9/L$)	> 100	
Hb (g/dL)	>11 (untransfused)	Not stated
Bone marrow lymphocytes (%)	>30 ; no nodules	Normal, allowing nodules or focal infiltrates
Partial Response (PR):		
Physical exam (nodes, and/or liver, spleen)	$\geq 50\%$ decrease	Downshift in stage
Plus ≥ 1 of:		
Neutrophils ($\times 10^9/L$)	≥ 1.5	
Platelets ($\times 10^9/L$)	>100	
Hemoglobin (g/dL)	>11 or 50% improvement	
Duration of CR or PR	≥ 2 months	Not stated
Progressive disease (PD):		Upshift in stage
Physical exam (nodes, liver, spleen)	$\geq 50\%$ increase or new	
Circulating lymphocytes	$>50\%$ increase	
Other	Richter's syndrome	
Stable disease (SD):	All others	No change in stage

Bone Marrow Examination

A bone marrow aspirate and biopsy are generally not required to make the diagnosis of CLL. Nevertheless, CLL is a disease of the bone marrow, and it is appropriate to evaluate a major site of involvement. The aspirate smear must show $\geq 30\%$ of all nucleated cells to be lymphoid. A bone marrow examination also provides useful prognostic information by determining whether there is diffuse or non-diffuse involvement, and permits an assessment of the erythroid precursors and megakaryocyte.

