8.0 STATISTICAL CONSIDERATIONS

8.1 Datasets to be Analyzed

The primary study endpoint is response to therapy (defined as a CR, or PR, and progression free survival). The secondary endpoints are toxicity, overall survival, complement levels (CH50 and C2 levels) will be measured from the time of entry into the clinical trial.

Toxicity information recorded will include the type, severity, time of onset, time of resolution, and the probable association with the study regimen. Tables will be constructed to summarize the observed incidence by severity and type of toxicity.

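### Section 7.2 prints two conflicting sets of response criteria and does not say which governs the primary endpoint; one complete-response marrow cell also appears reversed

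*Combined protocol and SAP*

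**What the plan says.** Section 8.1 reads "The primary study endpoint is response to therapy (defined as a CR, or PR, and progression free survival", closing the bracket there. Section 8.2 bases its two-stage decision on CR + PR. The criteria themselves appear only in section 7.2, in a table with an NCI-WG column and an IWCLL column:

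- **PR.** NCI-WG: a decrease of at least 50% in nodes, liver or spleen, plus at least one of three blood-count criteria. IWCLL: "Downshift in stage".
- **PD.** NCI-WG: an increase of at least 50% or new disease on examination, lymphocytes up by more than 50%, or Richter's syndrome. IWCLL: "Upshift in stage".
- **"Duration of CR or PR".** NCI-WG: at least 2 months. IWCLL: entered as not stated.
- **CR, marrow lymphocytes (%).** NCI-WG: ">30 ; no nodules". IWCLL: normal, with nodules or focal infiltrates allowed.

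Below the table, the paragraph on marrow examination says the aspirate must show at least 30% "of all nucleated cells to be lymphoid". Footnote 1 to the calendar in section 7.1 says: "If the BM biopsy is positive at baseline it must be repeated once to confirm CR". It adds: "If the BM biopsy is negative at baseline, it will not be repeated".

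**The concern.** A response endpoint needs one rule. Here the plan gives two and adopts neither in the objectives, the calendar, section 7.2 or section 8. The trial is open-label and single-arm, so a column chosen after the data are seen would be an undeclared analysis choice on the primary endpoint. Because PD is defined only in this table, PFS dates depend on the same choice.

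The marrow cell is a second and smaller matter. Read literally, NCI-WG complete response needs a marrow in the range that the same section associates with CLL, and a cleared marrow would fail.

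**Working it through.** **1. Do the columns classify the same patient differently?** The comparison uses only cells that are filled in both columns. Blank IWCLL cells may be merged cells and are not relied on.

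| Patient | NCI-WG | IWCLL |
|---|---|---|
| Nodes halved, neutrophils at least 1.5, sustained beyond 2 months, stage unchanged | PR | SD (no change in stage) |
| Nodes halved, neutrophils at least 1.5, stage falls, response lost before 2 months | Not PR, if the duration row is a requirement | PR |
| Nodes up by half and lymphocytes up by more than 50%, stage unchanged | PD | SD |

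The first two rows change the response count, in opposite directions. The third changes a PFS event.

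**2. Does any other text choose a column?** The objectives, the calendar and its footnotes, section 7.2, sections 8.1 to 8.4 and the data forms in Appendix 3 do not. Section 10.0 lists an NCI-WG guideline from 1996 and a later IWCLL update of it, but section 7.2 cites neither.

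**3. The marrow cell.** Three places in the plan bear on it: the 30% lymphoid level in the marrow paragraph, the normal marrow in the adjacent IWCLL cell, and footnote 1, where only a positive baseline marrow is repeated to confirm CR. Footnote 1 implies that a CR marrow is one that is no longer positive. All three point away from a requirement above 30%. The effect on CR + PR is small because PR has no marrow row. A patient denied CR on marrow alone would normally still have the reduction on examination and a qualifying count, and so would be PR. The exception is a patient with nothing enlarged at baseline.

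**4. Size under the section 8.2 rule for 36 patients.** Inputs from section 8.2: first stage 17 patients, stop at 4 or fewer; final total 36, active at 14 or more; null 25%, target 45%. Let b(x; n, p) be the binomial probability of x responders among n.

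- Plan's own figures. P(active) = sum over x = 5 to 17 of b(x; 17, p) × P(at least 14 − x of 19). This gives 4.4% at 25% and 80.0% at 45%, which meets the stated 5% and 80%.
- Total exactly 13 after passing stage 1, where one more responder would change the verdict: sum over x = 5 to 13 of b(x; 17, p) × b(13 − x; 19, p) = 4.0% at 25%, 6.7% at 45%.
- Total exactly 14, where one fewer would change it: the same sum with 14 in place of 13 and x = 5 to 14 = 2.3% and 9.5%.

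**5. The interim boundary.** P(exactly 4 of 17) is 22.1% at 25% and 4.1% at 45%. P(exactly 5 of 17) is 19.1% and 8.7%. These concern the step to stage 2 only. To change the final verdict by this route, the second stage must also bring the total to 14, which means at least 9 of 19 (2.9% at 25%, 50.6% at 45%):

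- Exactly 4, reclassified to 5: 22.1% × 2.9% = 0.6%; 4.1% × 50.6% = 2.1%.
- Exactly 5, reclassified to 4: 19.1% × 2.9% = 0.6%; 8.7% × 50.6% = 4.4%.

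These figures apply only if 36 are enrolled. Other places in the plan say 12, and 14 responses cannot be reached with 12. That conflict is a separate point.

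**The case against.** The strongest reply is that the two columns are not equally plausible. The NCI-WG column gives counts, duration, PD and SD in usable form. The IWCLL column says not stated in two cells and rests PR, PD and SD on stage without naming a staging system; the two systems mentioned in section 2.1 are background only. A site would probably work from NCI-WG. That stands, and it narrows the practical uncertainty. It does not close the gap, because the plan does not adopt NCI-WG.

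It is also fair to say that the marrow sign is one character in a table read from PDF, so an extraction error cannot be excluded. That is why the point here is to check the original table.

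Three stronger readings are tempting and not supported:

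- *A 22% chance of a changed decision.* That is the probability of sitting on the interim boundary under the null. The chance of a changed final verdict by that route is 0.6%. Section 8.2 also says only that the investigator may conclude inactivity at that step.
- *An inflated type I error.* If the measured rate under the null rose from 25% to 30%, P(active) would go from 4.4% to 15.5%. The 5-point shift is an assumption. The argument also needs the 25% benchmark to have been measured under the stricter criteria, and section 8.2 does not say which criteria produced it.
- *A proven overlap of PR and PD within NCI-WG.* Halved nodes, adequate neutrophils and lymphocytes up by more than 50% meet both only if any single PD row suffices. The table does not say so, although it does print such a connector for PR.

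**Conclusion.** The concern holds on its main point. The primary response count and PFS are defined by two rules that disagree in filled cells, and the plan selects neither. This should be fixed before analysis.

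How often the columns would disagree is unknown. What can be stated is sensitivity: with 36 patients, the final verdict hangs on one patient with probability 4.0% (total 13) or 2.3% (total 14) at a true 25%, and 6.7% or 9.5% at a true 45%. These rest on the printed 17/36 rule, applied as binding, and independent binomial responses.

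The marrow cell appears reversed and is at odds with the rest of sections 7.1 and 7.2. Its reach is the CR rate, the split between CR and PR, and the CR duration named in section 8.3. A reader might infer that it undermines the primary response rate; it does not, because PR has no marrow row. The documents do not state the correct value, so none is offered here.

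**What to change.** Before analysis, amend section 7.2 as follows:

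1. Name one column as the sole definition of CR, PR and PD for both response and PFS, and cite the matching guideline from section 10.0.
2. State whether the 2-month duration row must be met for a response to count.
3. If the IWCLL column is chosen, name the staging system.
4. Check the NCI-WG marrow cell against the original table and the cited guideline, and reconcile it with the marrow paragraph and footnote 1 of section 7.1. It need not match the IWCLL cell, which allows nodules.
5. Optionally, say how a patient who meets both a PR row and a PD row at one assessment is classed.

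The cost is a source check, one citation and a few sentences. No extra assessments are needed.

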7.3 Safety Assessments

7.3.1 Liver chemistry stopping and follow-up criteria

Liver chemistry stopping and follow-up criteria have been designed to assure subject safety and evaluate liver event etiology. The sponsor-investigator will review all events which meet liver chemistry stopping criteria to determine if the event was due to:

- tumor lysis, disease related liver involvement
- other identified cause and to exclude drug induced liver injury (DILI) due to ofatumumab

The criteria are relevant for all Ofatumumab studies because transient elevations in LFTs may be due to tumor lysis which is of clinical benefit, disease related liver involvement or due to other chemotherapy rather than drug induced liver injury from ofatumumab.

If the event is determined to be due to causes other than ofatumumab DILI and improvement is observed after withdrawal of ofatumumab, rechallenge may be attempted if deemed appropriate by the sponsor-investigator and in addition to consent of the subject.

7.3.1.1 Liver chemistry interruption/stopping criteria

1. ALT $>3\times\text{ULN}$ **and** bilirubin $> 2 \times \text{ULN}$ ($>35\%$ direct bilirubin; bilirubin fractionation required*)
2. ALT $>8\times\text{ULN}$
3. ALT $>5\times\text{ULN}$ for more than 2 weeks

***NOTE:** If serum bilirubin fractionation not immediately available, study drug should be discontinued if ALT $> 3 \times \text{ULN}$ and bilirubin $> 2 \times \text{ULN}$. Serum bilirubin fractionation should be performed if testing is available. If testing is unavailable, record presence of detectable urinary bilirubin on dipstick, indicating direct bilirubin elevations and suggesting liver injury.

When any of the liver chemistry stopping criteria is met, do the following:

- Immediately stop study treatment
- Hold Ofatumumab for two weeks, repeat liver chemistry testing at least twice weekly, and report to sponsor-investigator to discuss the possibility of re-challenging with ofatumumab. *Note: The 2 week time point for stopping medication was chosen because it will distinguish from LFT elevations due to tumor lysis which should have resolved within this time period. Medication is interrupted and it is a clinical and patient decision if ofatumumab may be re-started. The risk: benefit ratio is different in an oncology setting and an efficacious therapy may be life-saving.*
- Report SAE to Novartis within 24 hours

- All events of ALT > 3xULN **and** bilirubin > 2xULN (>35% direct bilirubin) (or ALT>3xULN and INR>1.5, if INR measured; INR measurement is not required and the threshold value stated will not apply to subjects receiving anticoagulants), termed 'Hy's Law', **must be reported as an SAE (excluding studies of hepatic impairment or cirrhosis).**
- NOTE: if serum bilirubin fractionation is not immediately available, study treatment should be discontinued if ALT > 3xULN **and** bilirubin > 2xULN. Serum bilirubin fractionation should be performed if testing is available. If testing is unavailable, **record presence of detectable urinary bilirubin on dipstick**, indicating direct bilirubin elevations and suggesting liver injury.

Liver chemistry follow-up assessments are to be followed until liver chemistries resolve, stabilize or return to baseline values.

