7.3.1.2. Liver Chemistry Follow-up Assessments

Chemistry tests/ assessments below are to be performed at the time of the event and then continued and/or discontinued at the discretion/judgment of the sponsor-investigator; please refer to stopping criteria within this document.

Viral hepatitis serology including:

- Hepatitis A IgM antibody;
- Hepatitis B surface antigen and Hepatitis B Core Antibody (IgM);
- Hepatitis C RNA;
- Cytomegalovirus IgM antibody;
- Epstein-Barr viral capsid antigen IgM antibody (or if unavailable, obtain heterophile antibody or monospot testing);
- Hepatitis E IgM antibody
- Serum creatine phosphokinase (CPK) and lactate dehydrogenase (LDH)
- Fractionate bilirubin, if total bilirubin >2xULN
- Obtain complete blood count with differential to assess eosinophilia
- Record the appearance or worsening clinical symptoms of hepatitis, or hypersensitivity, fatigue, decreased appetite, nausea, vomiting, abdominal pain, jaundice, fever, or rash
- Record use of concomitant medications, acetaminophen, herbal remedies, other over the counter medications, or putative hepatotoxins
- Increased alcohol use

The following assessments are required for subjects with ALT >3xULN and bilirubin >2xULN (.35% direct) but are optional for other abnormal liver chemistries:

- Anti-nuclear antibody, anti-smooth muscle antibody, and Type 1 anti-liver kidney microsomal antibodies
- Liver imaging (ultrasound, magnetic resonance, or computerized tomography) to evaluate liver disease.

Stopping Criteria:

- For subject meeting liver stopping criteria 1:
 - A repeat of liver chemistries within 24 hours, liver event follow-up assessments and close monitoring
 - A specialist or hepatology consultation is recommended
 - Monitor subjects twice weekly until liver chemistries (ALT, AST, alkaline phosphatase, bilirubin) resolve, stabilize or return to within baseline values.
- For subjects meeting criteria 2 or 3:
 - A repeat of liver chemistries within 24 to 72 hours for repeat liver chemistries and liver event follow-up assessments
 - Monitor subjects weekly until liver chemistries (ALT, AST, alkaline phosphatase, bilirubin) resolve, stabilize or return to within baseline values
- After holding ofatumumab for two weeks:
 - If the treatment is exhibiting efficacy **and** the subject wants to continue therapy after being informed of the results of liver chemistry testing, then the ofatumumab may be re-started.

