 - Liver chemistries and follow-up assessments should be monitored at a minimum of every 2 weeks until resolution, stabilization, or a return to baseline values, at which point monitoring should be continued per protocol
- Subjects with $ALT > 3 \times ULN$ **but** $< 5 \times ULN$ **and** bilirubin $< 2 \times ULN$ without hepatitis symptoms or rash, and who may be monitored weekly for at least 4 weeks, then the following actions should be taken:
 - Subjects can continue ofatumumab
 - Weekly repeat of liver chemistries until they resolve, stabilize, or return to baseline values, then monitor liver chemistries as per protocol assessment schedule

If at any time the subject meets any of the liver chemistry stopping criteria, then proceed as described above.

If after 4 weeks of monitoring, $ALT < 3 \times ULN$ and $\text{bilirubin} < 2 \times ULN$ monitor twice monthly until liver chemistries normalize or return to within baseline values

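### An ALT and INR finding that the protocol itself calls Hy's Law requires an SAE report but no mandatory ofatumumab hold

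*Combined protocol and SAP*

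**What the plan says.** Section 7.3.1.1 lists three numbered stopping criteria: (1) ALT >3xULN with bilirubin >2xULN, more than 35% direct; (2) ALT >8xULN; (3) ALT >5xULN for more than two weeks. The actions follow the words "When any of the liver chemistry stopping criteria is met, do the following". They include an immediate stop and the instruction "Hold Ofatumumab for two weeks, repeat liver chemistry testing at least twice weekly".

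The same list defines Hy's Law, which must be reported as an SAE. One arm is the combination in criterion 1. The other reads "or ALT>3xULN and INR>1.5, if INR measured; INR measurement is not required", and its threshold does not apply to subjects on anticoagulants.

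Section 7.3.1.2 has a separate rule for ALT >3 but <5xULN with bilirubin <2xULN, no hepatitis symptoms or rash, and weekly monitoring possible: "Subjects can continue ofatumumab", with "Weekly repeat of liver chemistries until they resolve, stabilize, or return to baseline values". The rule has no INR condition. Its override is "If at any time the subject meets any of the liver chemistry stopping criteria, then proceed as described above".

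The study calendar (section 7.1, footnote 7) puts INR in the scheduled liver chemistry panel. Exclusion criterion 16 in section 3.3 bars subjects receiving warfarin.

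**The concern.** The two arms share one name and one reporting duty, but they lead to different treatment of the subject. The bilirubin arm forces an immediate stop. The INR arm forces a report and nothing more, and in part of its range the protocol expressly permits the next dose. Because INR is scheduled, this arm can be triggered in the trial. At stake is the safety of an individual subject: further 2000 mg doses while an event that the protocol labels Hy's Law has had no mandatory pause and no dedicated review of whether the drug caused it. The response endpoint, the sample size and the trial's conclusions are not affected.

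**Working it through.** The plan states no figure on this point, so the check applies its rules to defined cases and then counts doses.

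**Step 1. Which rules fire.** All cases are without anticoagulants. Case A is one example: ALT 4xULN, bilirubin 1.5xULN, INR 1.8, no hepatitis symptoms or rash, weekly monitoring possible.

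| | A: the example above | B: ALT 5 to 8xULN for 2 weeks or less, bilirubin not above 2xULN, INR >1.5 | C: ALT >3xULN, bilirubin >2xULN, >35% direct |
|---|---|---|---|
| Criterion 1 | no (bilirubin) | no (bilirubin) | yes |
| Criterion 2 | no (4 < 8) | no (not above 8) | not needed |
| Criterion 3 | no (4 < 5) | no (duration) | not needed |
| Hy's Law SAE | yes, INR arm | yes, INR arm | yes, bilirubin arm |
| Continue rule | met | not met (ALT not <5) | not met |
| Result | may continue | neither stop nor continue rule | immediate stop, two-week hold |

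Above 8xULN, or above 5xULN for more than two weeks, criterion 2 or 3 imposes the hold whatever the INR. The gap is therefore confined to A-type and B-type subjects.

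**Step 2. What A and B still have.** The SAE goes to the drug supplier within 24 hours (section 7.4.6). The probable association with the regimen is recorded (section 8.4). The principal investigator and coordinator meet at least monthly, and the safety committee reviews new drug-related SAEs monthly (section 9.6). The investigator may withdraw the subject for medical reasons (section 3.4). The general work-up may also apply, since "Chemistry tests/ assessments below are to be performed at the time of the event" is not tied to a criterion number. A-type subjects also have weekly liver chemistries.

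**Step 3. What A and B lack.**
- The mandatory two-week hold.
- The section 7.3.1 review to exclude drug-induced liver injury, which covers only events meeting the stopping criteria.
- The criterion 1 escalation in section 7.3.1.2: repeat chemistries within 24 hours, a recommended specialist or hepatology consultation, and twice-weekly monitoring.

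Over two weeks, monitoring under the continue rule is 2 × 1 = 2 panels. Under criterion 1 it is at least 2 × 2 = 4; the 24-hour repeat may be one of these. Footnote 7 suggests that the weekly repeats include INR, but the list of values followed to resolution in section 7.3.1.2 names only ALT, AST, alkaline phosphatase and bilirubin.

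**Step 4. Doses a hold would delay.** Nominal dosing weeks are 1 to 8, 12, 16, 20 and 24 (section 7.1). Dose 1 is 300 mg and the rest are 2000 mg (section 4.0). Suppose the finding is known before dosing at week w. The low count takes doses from w up to, but not including, w+2; the high count also includes w+2.

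| Week w | Doses delayed | Amount |
|---|---|---|
| 2 to 6 | 2 to 3 | 2 × 2000 = 4000 mg to 3 × 2000 = 6000 mg |
| 7 | 2 (weeks 7 and 8; none at 9) | 4000 mg |
| 8, 12, 16, 20, 24 | 1 | 2000 mg |

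Week 1 is left out because a pre-dose result there precedes any ofatumumab. Footnote 7 schedules panels every two weeks in the first month and then monthly, so not every dosing week has a planned draw, and section 7.1 allows visits to move by 7 business days either way. The table shows what a hold would delay at a given week, not how often that would happen.

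**The case against.** The best defence is that a reporting threshold may properly be wider than a stopping threshold. The INR arm is conditional on INR being measured, which suits a reporting trigger. Section 7.3.1 warns that liver test rises may reflect tumor lysis, and section 7.3.1.1 says that risk and benefit weigh differently in oncology. This would persuade if the whole Hy's Law definition were for reporting only. But its other arm already forces a stop, and the protocol gives no reason to treat the INR arm differently. The tumor lysis argument favors a hold: section 7.3.1.1 chose two weeks because lysis-related rises should resolve in that time.

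A second defence is that the Hy's Law text sits in the list headed by the stop instruction, so a hold is implied. Some sites may read it so. The heading, however, applies only once a criterion is met, and INR is in none. Events meeting a criterion are already SAEs under section 7.4.4, so the INR arm adds a report only for subjects who meet no criterion.

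Three points on the other side stand. The case is rare. Continuation is permitted, not required. And plasma matters: two units precede each ofatumumab dose from dose 2 (sections 4.0 and 7.1), and section 2.4 says plasma supplies coagulation factors, so an INR drawn after plasma could be altered and hide a case. An INR rule must state when the sample is taken.

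A reader might go further and infer that these subjects are dosed without oversight, or that the plan requires dosing to go on. The documents support neither, given the safeguards in step 2 of the working. Nor do they show that autoantibodies and liver imaging must become compulsory here. Section 7.3.1.2 requires them for the ALT and bilirubin combination, "but are optional for other abnormal liver chemistries"; they can still be ordered, and making them mandatory would add procedures beyond what closes this gap.

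**Conclusion.** The inconsistency is real and should be corrected. The protocol names a liver event Hy's Law and requires its report, yet no stopping criterion captures the INR arm. For ALT >3 to <5xULN, with the other conditions of the continue rule met, it expressly allows dosing; for ALT 5 to 8xULN lasting two weeks or less it is silent. The gap is the absence of the mandatory hold, the drug-injury review and the criterion 1 escalation, not of all supervision.

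Its size is small in expectation. The documents give no event rate, and few cases are expected among about 12 subjects. For a subject affected in the weekly phase, the permitted exposure that a hold would have delayed is up to 2 to 3 doses; in the 4-weekly phase it is 1 dose. These counts assume nominal visit weeks and a result known before dosing. The effect of plasma on INR cannot be quantified from the documents.

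**What to change.** Four wording changes:

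1. In section 7.3.1.1, add the stopping criterion *ALT >3xULN and INR >1.5 (subjects not on anticoagulants; INR drawn before that visit's FFP)*, handled as criterion 1. This covers both the ALT >3 to <5xULN and the 5 to 8xULN cases, and it brings in the section 7.3.1 review.
2. In the section 7.3.1.2 continue rule, add *and INR <=1.5 (subjects not on anticoagulants)*.
3. In section 7.3.1.2, add INR to the values followed to resolution for the new criterion.
4. In section 7.3.1.1, delete the statement that INR measurement is not required, which conflicts with footnote 7 of the study calendar.

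Leave autoantibodies and liver imaging optional for this group. That block is keyed to the bilirubin combination and not to a criterion number, so handling the new criterion as criterion 1 does not change it.

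Cost: an amendment to the text and attention to drawing INR before plasma. INR is already scheduled, so no new routine test is needed; a subject who meets the criterion has the closer follow-up of criterion 1. The clinical downside is a rare two-week hold, which is reversible because sections 7.3.1 to 7.3.1.2 already allow restart.
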